All volunteers will undergo medical history taking and examination. Inclusion and exclusion criteria are detailed below. Basic investigations performed prior to inclusion will comprise height and weight measurement, blood tests (full blood count, urea and electrolytes, liver function tests, thyroid function tests and plasma glucose) and an electrocardiogram. Where other blood tests have been performed as part of routine clinical care, these results may be accessed by the clinical research team.

Informed consent is considered a crucial part of the study. All of the research doctors undertaking this process are medically qualified and experienced in taking informed consent for human research studies according to GCP guidelines.

Inclusion criteria for patients with conditions of interest

- Age >18 years
- Diagnosed with a condition known to be associated with prolonged exposure to endogenously elevated gut hormones or likely to be associated with increased energy expenditure and/or BAT activation.

Exclusion criteria for patients with conditions of interest

- As for Objective 1, but allowing for the primary condition of interest.
- Pregnancy.

Patients with conditions of interest visits

Each patient will attend their first study visit on the same day they are recruited from an Outpatient Clinic. Up to 5 subsequent follow-up visits will then be scheduled to investigate the effect of treatment of the underlying condition over time on EE and/or BAT activation. Therefore each patient will be invited to attend a maximum of 6 study visits.

Each study visit will consist of a single 20 ml blood sample, thermal imaging (with or without cold stimulation, as described above) for up to 30 minutes and indirect calorimetry (as described above) for

up to 60 minutes. Premenopausal females will be asked to take a urine pregnancy test at each study visit to exclude pregnancy. The participants with medical conditions of interest will not have intravenous cannulae inserted. They will not be subjected to any gut hormone or saline infusions, and they will not have any PET-CT scans as part of this study. However if the patient has one or more PET-CT scans as part of their routine clinical care, then analysis of the scan(s) will be included in the study providing the region of interest (supraclavicular area and neck) is included in the scan(s).

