The most common minor side effect (although still rare) of glucagon infusion is mild nausea. This effect is even less likely to occur in this study, which proposes to use doses that produce physiological post-prandial plasma levels in fasted subjects. If nausea does occur, it wears off very quickly when the infusion is discontinued, because this peptide hormone is significantly metabolised within minutes. If a volunteer experiences this side effect then no further infusions of glucagon will be administered to that volunteer.

ADVERSE EVENTS

An adverse event is any untoward medical occurrence in a patient or clinical study subject. A serious adverse event is an adverse event that results in death, is life-threatening, requires hospitalization or prolongs an existing inpatient's hospitalization, results in persistent or significant disability or incapacity, or is a congenital anomaly or birth defect. All non-serious adverse events will be recorded in the Trial Master File. If a serious adverse event occurs, a serious adverse event form will be completed and sent to the Chief Investigator and the Sponsor within 24 hours. All serious adverse events that are unexpected and related to the study will be reported to the Local Research Ethics Committee. Serious adverse events will be reported as required by their Local Research Ethics Committee, Sponsor and/or Research & Development Office.

Although no serious adverse effects are anticipated, any such effect will terminate the arm of the study during which the serious adverse effect occurred.

DATA HANDLING

The Chief Investigator will preserve the confidentiality of participants taking part in the study and is registered under the Data Protection Act. Personal contact details are required for communication with the subjects participating in the study. This information is held solely for communication between the researchers and participants. Details stored on university computers will be password protected and will only be accessed by the researchers involved in the study. Personal identifiers will be deleted 6 months after the participant has completed their involvement in the study.

Information held on NHS computers is solely for the purpose of hospital booking and routine sample collection and analysis (e.g. for medical screening). This information is password protected in a similar manner to that of other hospital patients.

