Subjects will be given a personal study code number which will be used throughout the study and in the analysis of data. Coded samples or images will also be treated with confidentiality when undergoing analysis. Analysis will take place in the Imanova Clinical Imaging Centre and the Department of Investigative Medicine at Hammersmith Hospital and be carried out by the researchers themselves. The data will be kept in a secure environment in these departments, under the authority of [name]. Data will be stored for 15 years after completion of the study. Only the researchers will have access to this data.

REGULATORY COMPLIANCE

The Chief Investigator has obtained approval from the xxx Research Ethics Committee. The study has been submitted for Site Specific Assessment (SSA) at each participating NHS Trust. The Chief Investigator will obtain a copy of the Trust R&D approval letter before accepting participants into the study. The study will be conducted in accordance with the recommendations for physicians involved in research on human subjects adopted by the 18th World Medical Assembly, Helsinki 1964 and later revisions.

Consent to enter the study will be sought from each participant only after a full explanation has been given, an information leaflet offered and time allowed for consideration. Signed participant consent will be obtained. The right of the participant to refuse to participate without giving reasons will be respected. After the participant has entered the study the clinician remains free to give alternative treatment to that specified in the protocol at any stage if he/she feels it is in the participant's best interest, but the reasons for doing so should be recorded. In these cases the participants remain within

the study for the purposes of follow-up and data analysis. All participants are free to withdraw at any time from the protocol treatment without giving reasons and without prejudicing further treatment.

The study may be subject to inspection and audit by Imperial College London under their remit as sponsor and other regulatory bodies to ensure adherence to GCP and the NHS Research Governance Framework for Health and Social Care (2nd edition).

FUNDING AND INDEMNITY

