**NCT No. NCT01935791**

## Statistical Analysis

Based on previous studies of the hormonal and cold exposure effects on human BAT activity 1, 2, we calculated that, for an equivalent rise in EE, a sample size of 4 per group (glucagon versus control) would have 95% power to detect a significant difference between the effects of cold exposure and glucagon using F-FDG PET/CT in confirmed BAT-positive volunteers. Because of safety considerations, as PET/CT scans expose healthy patients in this study to ionising radiation, we limited this study to males only and to the smallest possible sample size to answer our initial question about the differential effects of cold exposure and glucagon administration on human BAT activity for a given rise in EE.

All data were analysed using GraphPad Prism 6 software (GraphPad Software, Inc., San Diego, CA, USA). Results are presented as means ± standard error of the mean. One-way repeated measures anova with Tukey's test was used to compare differences between the three intervention groups. A p value < 0.05 was considered to indicate statistical significance.

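### For Objective 1, Visits 1-3, the SAP's repeated-measures ANOVA uses only volunteers with all three conditions and has no rule for a missing visit; a mixed model would keep the rest

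*SAP*

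**What the plan says.** The SAP, Statistical Analysis, gives one inferential method, a one-way repeated-measures ANOVA, with which Tukey's "test was used to compare differences between the three intervention groups". On software it says "All data were analysed using GraphPad Prism 6 software", and on the threshold "A p value < 0.05 was considered to indicate statistical significance". It defines no analysis set, gives no rule for a volunteer with a missing or unusable visit, and names no alternative model.

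The Protocol, Study Visits for Objective 1, has three conditions in Visits 1-3, given to each volunteer in random order: saline at thermoneutrality, saline with cold, and glucagon. The PET-CT pair (Visits 4 and 5) and the MRI pair (Visits 6 and 7) have two conditions each. Under the Protocol, therefore, the three-way comparison fits Visits 1-3.

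The Protocol, Recruitment for Objective 1, plans for 20 volunteers with 16 completing the arm. Regulatory Compliance lets any participant withdraw at any time and does not say how a withdrawn participant's data are analysed.

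**The concern.** A classical one-way repeated-measures ANOVA works on a full volunteer-by-condition table. If one cell is empty, the whole row goes. A volunteer with usable thermoneutral and cold visits but no usable glucagon visit still informs the cold-versus-thermoneutral contrast directly, and the glucagon contrasts indirectly, yet he contributes nothing to the named test.

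The Protocol expects that not everyone will finish, so the SAP should say what happens to such volunteers. Without a rule they are either dropped or handled in some unstated way, and a reader of the results cannot tell which. At stake are some precision in a small crossover study and clarity about who is in the comparison.

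**Working it through.** **The plan's own figures.** The recruitment figure is consistent with 20% non-completion: 16 / (1 - 0.20) = 20. It covers the whole arm, including the step that sends only responders on to Visits 4-7, so it is not a missing-visit rate for Visits 1-3. The SAP also states that "a sample size of 4 per group (glucagon versus control) would have 95% power to detect a significant difference". That cannot be reproduced, because no effect size or SD is given. It also concerns PET/CT rather than the three-way comparison, so it is not used here.

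**Assumption.** Neither document counts missing visits. For illustration, take 20 volunteers, of whom 4 each miss exactly one of Visits 1-3.

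**Visits used.**
- Observed: 20 x 3 - 4 = 56.
- Used by the complete-case ANOVA: 16 x 3 = 48.
- Discarded: 56 - 48 = 8, and 8/56 = 14.3%.
- If each of the 4 misses two visits instead: observed 52, used 48, discarded 4, and 4/52 = 7.7%. A single remaining visit carries no within-volunteer contrast, so little precision is lost in that case.

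**Contrast variance**, in units of the within-volunteer error variance, from a least-squares model with volunteer and condition effects. A volunteer observed in all three conditions adds 1/3 to the weight of each pair of conditions; one observed in two conditions adds 1/2 to that pair. With total weights `w`:

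`Var(a - b) = 1 / [ w_ab + w_ac * w_bc / (w_ac + w_bc) ]`

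*16 complete cases.* Every weight is 16/3 = 5.333. Var = 1 / (5.333 + 2.667) = 0.125.

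*All 56 visits, missing visits spread over conditions* (two volunteers miss condition 1, one misses condition 2, one misses condition 3):
- w23 = 5.333 + 1 = 6.333; w12 = w13 = 5.333 + 0.5 = 5.833.
- Var(2 - 3) = 1 / (6.333 + 2.917) = 0.108, which is 13.5% below 0.125.
- Var(1 - 2) = Var(1 - 3) = 1 / (5.833 + 3.037) = 0.113, which is 9.8% below.

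*All 56 visits, all four missing glucagon:*
- w(saline, cold) = 5.333 + 2 = 7.333; both glucagon weights are 5.333.
- Glucagon contrasts: 1 / (5.333 + 3.088) = 0.119, which is 5.0% below.
- Cold versus thermoneutral saline, which lost no visits: 1 / (7.333 + 2.667) = 0.100, which is 20% below.

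For contrasts that lost visits, the variance is thus about 5-14% lower. The standard error is about 2.5-7% lower (square roots of 0.950 and 0.865 are 0.975 and 0.930).

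**Range for the assumption.** If each visit is independently usable with probability p = 0.90 to 0.95 (also assumed), the share with all three is p^3 = 0.73 to 0.86, or 14.6 to 17.1 of 20. The illustration's 16 lies inside that range. The share of usable visits discarded is 1 - p^2 = 0.19 to 0.10. This counts visits and overstates the loss of precision.

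**The case against.** The strongest reply is that no visit is shown to be missing. If every analysed volunteer had all three visits, the ANOVA loses nothing. The 16-of-20 figure includes volunteers who might finish Visits 1-3 and then not go on. All of that stands, and it is why the size is given only as an illustration. It does not supply the missing rule. A sponsor who prefers complete cases could close the gap in reporting by saying so and listing exclusions, but would still forgo the extra precision.

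Four stronger readings are tempting, and the documents do not support them.

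- *The SAP contradicts the Protocol.* Regulatory Compliance keeps participants in "the study for the purposes of follow-up and data analysis", but only where a clinician has given treatment other than that specified. It does not speak of missed visits, and the sentence on withdrawal says nothing about analysis.
- *The ANOVA discards Objective 2 patients.* For them, "Up to 5 subsequent follow-up visits will then be scheduled", so visit numbers vary. But they receive no infusions and are not among the three intervention groups. The Objective 2 gap is that the SAP names no analysis at all, which is a separate matter.
- *Nausea removes the glucagon condition, so the comparison is biased towards tolerant volunteers.* After nausea, "no further infusions of glucagon will be administered to that volunteer". Glucagon is given once in Visits 1-3, so this rule mainly affects the later PET-CT and MRI visits. An infusion stopped early could leave that visit incomplete, but the documents do not say that it would. For discomfort with cold, the Protocol describes warming or removing the vest, not losing the visit.
- *Collected data were discarded.* That is a possible consequence of the method, not something the documents report.

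**Conclusion.** The point holds for Objective 1, Visits 1-3. The named test is a complete-case method, the SAP states no rule for an incomplete volunteer, and the Protocol foresees non-completion. A better method is available at little cost.

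The size is modest. With 4 of 20 volunteers each missing one visit, 8 of 56 observed visits (14%) are discarded, and using them would lower the variance of the affected contrasts by about 5-14%. This rests on an assumed number and pattern of missing visits, on reading the three intervention groups as the Visits 1-3 conditions, and on equal error variance across conditions. That the classical ANOVA needs complete data is a property of the method, which the SAP does not state. The documents do not establish bias in either direction.

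**What to change.** In the SAP, Statistical Analysis:

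1. Define the analysis set for Visits 1-3 as all volunteers with at least one usable visit, and report the number excluded or missing per condition, with reasons.
2. Fit a linear mixed model by REML to all available Visits 1-3 data, with condition as a fixed effect, participant as a random effect, and small-sample degrees of freedom such as Kenward-Roger. Keep Tukey-adjusted pairwise contrasts.
3. Show the complete-case repeated-measures ANOVA as a sensitivity analysis.

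With complete data and no visit term, the condition contrasts equal those of the ANOVA. If a visit-order term is added they may differ slightly. Equality would then need each condition to fall equally often at each visit position, which is impossible with 16 or 20 volunteers because neither number is divisible by 3.

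**Cost.** A change of SAP wording and software that fits mixed models; the SAP names only Prism 6, so the sponsor should check whether that suffices. No new data are needed. The model relies on data being missing at random given what was observed, so it does not remove bias from loss driven by tolerance. The reasons for exclusion should therefore be reported beside the result.
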